Successful execution of this study will lay the groundwork for a clinical trial to compare the efficacy of a clot-specific imaging modality (**thrombus body scan or TBS**) that has the potential to be more accurate for the diagnosis of VTE, better able to establish the total clot burden in the body with a single test and more widely applicable to patients with renal failure and lung disease.

III. SUBJECT SELECTION

A total of eighty (80) subjects will be recruited for this study, which will be performed at the Massachusetts General Hospital (MGH). All eighty (80) subjects will be studied with the same protocol: a single injection of ⁶⁴Cu-FBP8 and PET-CT imaging at least three hours after injection at four bed positions, which will provide the imaging data for fresh blood clot at the three locations covering all three specific aims.

Inclusion Criteria:

Each subject must meet the following criteria to be enrolled in the study:

- 18 years of age or older with a clinically significant pulmonary embolus (PE) confirmed by a filling defect in CT angiography (CTA), and
- Subjects must receive the radiotracer injection within 72 hours of their diagnosis.

Exclusion Criteria:

- Subjects < 18 years of age
- Time of expected radiotracer injection > 72 hours from the time of a positive venous duplex ultrasound or CT-angiogram,
- Women subjects of childbearing potential who are pregnant, seeking to become pregnant, or have a positive serum pregnancy (beta-HCG) test,
- Unable to lie flat for 45 minutes as assessed by physical examination and medical history (e.g. back pain, arthritis, dyspnea),
- Weight that exceeds the PET camera table limit (300 kg)
- The subject will not be enrolled in the study if the radiation exposure for research studies during the prior 12 months, combined with the exposure from this study would exceed 50 mSv.
- Due to the radiation exposure from imaging studies, all women of childbearing potential will be required to have a negative serum pregnancy test performed prior to any imaging procedures on the same day (if not already done that day). Patients with a positive serum pregnancy test will be excluded. Breast feeding women will also be excluded.
- A pre-existing condition or use of a medication including vasopressors and tPA (due to its effects on clot) that in the opinion of the investigator may place the subject at a substantially increased risk
- Hemodynamic instability, including requiring escalating doses of vasopressor medication.

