Patients will be contacted at 3, 6 and 12 months following the diagnosis of PE. Death and recurrence of DVT-PE will be assessed. Results of any imaging studies (CT angiograms, echocardiograms, or venous duplex ultrasound studies) and serologic studies (follow up d-dimer) will be collected and patients will undergo a survey to collect information about symptoms attributable to PE-DVT as well as quality of life using Standard Form 36,²⁸ VEINES QOL29 and the patient's self-assessment of their overall health status on a 1 – 10 scale, with 1 indicating the worst possible and 10 the best possible health. For patients followed at MGH this will be done in person at the end of their PERT or pulmonary clinic follow up clinic visit. For those followed elsewhere, this will be done by telephone with subjects and their treating physicians. NYHA functional class, 6-min walk distance, and change in pulse oximetry with walking will be assessed.

VI. BIOSTATISTICAL ANALYSIS

Once a patient is enrolled, the subjects will receive an injection of up to 10 mCi ⁶⁴Cu-FBP8 and imaged with CT-PET approximately at least 3 hours after injection, when the “target-to-background” ratio (TBR) of activity is expected to be high based on previous studies.²⁷ With CT-PET the attenuation correction is done using a low-dose CT volumetric scan. Afterwards, PET acquisitions of 10 min duration each are performed in four positions, thorax, pelvis and thighs (2 positions), which are used to assess regional ⁶⁴Cu-FBP8 activity.

Specific data variables:

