Specific Aim 2: The thrombus ROI, its volume and clot burden within the thigh ROI will be compared with the location and extent of the clot on venous duplex ultrasound. We will determine the number and location of the thrombus ROI(s) within the thigh ROI, and the overall clot burden as sum of ^{64}Cu -FBP8 activity within a thrombus ROI(s) within the thigh ROI. Additionally, we will quantify the volumes and locations of the thrombus ROIs of the PET scan and the venous duplex ultrasound relative to each other. Also, we will perform a vessel segmentation using the 3D Slicer (open source software) and determine the location of thrombus ROI(s) with the blood vessel.

Specific Aim 3: The prevalence of high ^{64}Cu -FBP8 fibrin activity in the pelvic ROI and upper extremity ROI's will be reported. Additionally, as a secondary analysis, both the total fibrin activity in the imaged fields, excluding the liver, gallbladder, kidneys and urinary bladder normalized by injected dose for all patients will be correlated with the plasma D-dimer drawn at the time of imaging. D-dimer levels will be drawn daily from the time of first diagnostic imaging to the fibrin probe imaging (up to 3 days maximum in total) as well as PT, PTT, platelets and fibrinogen. Anticoagulants used, as well as timing and dose will be carefully recorded during this period.

For all Specific Aims, death, VTE recurrence, and quality of life measures will be compared with the clot burden measured by PET and conventional imaging modalities, stratified by treatment (systemic thrombolysis, catheter thrombolysis, or heparin alone) using multiple correlation, ANOVA, and t-tests for pairwise comparisons.

VII. RISKS AND DISCOMFORTS

^{64}Cu -FBP8 PET probe:

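### Recurrence and death over 12 months are compared with PET clot burden, but anticoagulant status after the scan is neither a named follow-up item nor used in the analysis

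*Combined protocol and SAP*

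**What the plan says.** The anticoagulant item sits in Section VI, Outcome Measures, Specific Aim 3: "Anticoagulants used, as well as timing and dose will be carefully recorded during this period". The sentence before it fixes the period, since daily D-dimer and coagulation tests run "from the time of first diagnostic imaging to the fibrin probe imaging (up to 3 days maximum in total".

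Follow-up is in Section V, Follow up: "Patients will be contacted at 3, 6 and 12 months following the diagnosis of PE", and "Death and recurrence of DVT-PE will be assessed". The data list there is detailed. It begins "Results of any imaging studies (CT angiograms, echocardiograms, or venous duplex ultrasound studies) and serologic studies (follow up d-dimer) will be collected" and goes on to symptoms, two quality-of-life instruments, a self-rated health score, NYHA class, walk distance and oximetry. Anticoagulant use is not on it.

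Three items in Section V could reach further:

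- Footnote e under the Study Events table says that anticoagulants, timing and dosing are recorded, and gives no time window.
- The sources of research material include drug or mechanical treatment for VTE, without dates or a follow-up window.
- The Study Events table marks an EMR review at 3, 6 and 12 months, without stating its content.

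The closing paragraph of Outcome Measures says that, for all aims, "death, VTE recurrence, and quality of life measures will be compared with the clot burden measured by PET and conventional imaging modalities". The methods are multiple correlation, ANOVA and t-tests. The only control for treatment is stratification by systemic thrombolysis, catheter thrombolysis or heparin alone.

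**The concern.** The recurrence comparison covers a year, while the anticoagulant detail that Section VI specifies covers at most three days. Whether a patient is still anticoagulated can affect the risk of recurrence, and the decision to continue, switch or stop may depend on how much clot was seen. Section VIII gives one possible route: clot that PET shows where the treating team had not seen or evaluated it is reported to that team. The predictor under study can therefore reach the people who decide later treatment.

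The three treatment strata describe initial treatment. Within any of them, patients can stop or switch at different times. If stopping is related to burden, high burden could look protective when it has no effect, or a harmful effect could be diluted or reversed. If high-burden patients stop earlier, the error runs the other way. The study is meant to prepare a larger trial, so a misread prognostic signal could be carried forward.

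Correlation, ANOVA and t-tests also make no allowance for unequal follow-up or for death before recurrence.

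**Working it through.** **Figures in the plan.** "A total of eighty (80) subjects will be recruited for this study". Section VI gives no expected event rate, alpha, power or effect size, so there is no stated figure to reproduce. Every rate and proportion below is an assumption chosen for illustration.

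**Illustration 1: burden has no effect, and only stopping differs.**

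Risk over 12 months = (1 − p) × on + p × [on × t + off × (1 − t)]

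- on = 2% a year; off = 5% or 8% a year
- t = time of stopping, 0.25 or 0.5 year
- p = share stopping: 0.20 with high burden, 0.60 with low burden
- two burden halves of 40 subjects

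Example with off = 8% and t = 0.25:

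- High burden: 0.8 × 0.02 + 0.2 × (0.005 + 0.06) = 0.029
- Low burden: 0.4 × 0.02 + 0.6 × (0.005 + 0.06) = 0.047
- Ratio: 0.029 / 0.047 = 0.62

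| off | t | high | low | ratio | expected events in 80 |
|---|---|---|---|---|---|
| 5% | 0.50 | 2.30% | 2.90% | 0.79 | 0.92 + 1.16 = 2.08 |
| 5% | 0.25 | 2.45% | 3.35% | 0.73 | 0.98 + 1.34 = 2.32 |
| 8% | 0.50 | 2.60% | 3.80% | 0.68 | 1.04 + 1.52 = 2.56 |
| 8% | 0.25 | 2.90% | 4.70% | 0.62 | 1.16 + 1.88 = 3.04 |

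If the high-burden half stops more often instead (shares swapped), the ratios invert to between 0.029 / 0.023 = 1.26 and 0.047 / 0.029 = 1.62.

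**Illustration 2: wider assumptions, with status fixed for the year.**

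Risk = s × off + (1 − s) × on, where s is the share off anticoagulation. Twelve-month risks on/off are 2%/8%, 2%/10% and 3%/15%. The share off in low/high burden is 60%/30%, 70%/20% and 80%/10%.

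- *No burden effect.* At 2%/8% and 60%/30%: low 0.6 × 0.08 + 0.4 × 0.02 = 0.056; high 0.3 × 0.08 + 0.7 × 0.02 = 0.038; ratio 0.68. At 2%/10% and 80%/10%: 0.028 / 0.084 = 0.33. The full range is 0.33 to 0.68.
- *Burden truly doubles risk.* The same two cases give 0.076 / 0.056 = 1.36 and 0.056 / 0.084 = 0.67. The full range is 0.67 to 1.36.
- *Equal stopping (50%/50%).* The ratios are 1.00 and 2.00, so there is no distortion.
- *Chance of a nominally significant result.* With no burden effect and unequal stopping, about 4 to 7 events are expected. The probability of two-sided p < 0.05 is then about 6% to 27% (normal approximation, rough at these counts).

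**Sampling error, for scale.** With 1 versus 2 events in 40 per half, the ratio is 0.5. The standard error of its log is √(1/1 − 1/40 + 1/2 − 1/40) = √1.45 = 1.20, so the approximate 95% interval is 0.05 to 5.3.

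**The case against.** The strongest reply is that the plan may already collect what is needed. Footnote e has no time window, VTE drug treatment is a chart source, the EMR is reviewed at every follow-up, and for patients followed elsewhere the treating physicians are telephoned. This stands in part. A reader might infer that later anticoagulation goes unrecorded or can never be recovered; the documents do not support that. What they do show is that none of these items names status or stop dates after the scan, and that no analysis uses them.

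Second, sampling error swamps the bias. In Illustration 1 the two halves differ by only 0.24 to 0.72 of one event. This also stands. It rules out a complex model and makes the result descriptive with or without stop dates. It does not remove the need to know whether the few events occurred on or off treatment.

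Third, anticoagulation after PET follows the burden measurement and may lie downstream of it. The association under usual care is then a legitimate prognostic description. Conditioning on later treatment changes the question, and truncating follow-up at stopping can introduce informative censoring. This stands, and it is why neither analysis is asked for below.

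Fourth, this is one ancillary comparison in a proof-of-concept study, and all subjects are planned for 12 months of follow-up. That limits how much rests on the point.

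**Conclusion.** The point holds as a gap in data specification and method for one secondary comparison. Anticoagulant status after the scan is not named as a follow-up item and enters no analysis, although recurrence and death over a year are set against clot burden. If stopping or switching is related to burden, the association partly reflects later anticoagulation and could not be read as an effect of burden. The documents give no data on that relation; the reporting of PET findings to the treating team only makes it possible. The sizes shown (0.62 to 0.79 in the first illustration, 0.33 to 0.68 in the second, for a burden with no effect) rest wholly on assumed inputs and vanish if stopping is unrelated to burden.

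A reader might go further and conclude that the recurrence result will be uninterpretable or is likely to be falsely significant. The documents do not support that: some of the data may be retrievable, a descriptive reading under usual care remains possible, and with so few events a significant result is unlikely under most of the assumptions tried. The PET comparisons in Aims 1 and 2 and the Aim 3 correlation with D-dimer at imaging are unaffected.

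**What to change.** *Data.* At the existing 3-, 6- and 12-month contacts and EMR review, record whether an anticoagulant is being taken and which, the date and reason of any stop or switch, and the date of each recurrence or death. State that footnote e covers follow-up.

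*Analysis.* In Section VI, replace the t-tests and ANOVA for recurrence with time to first recurrence from PET, censored at last contact, with death as a competing event. List each event as on or off anticoagulation. Label the comparison descriptive, because few events are expected in 80 subjects. A time-varying anticoagulation model or truncation at stopping need not be required.

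*Cost.* A few fields on contacts that already take place, and some wording in Section VI. The contacts become slightly longer and the statement about recurrence more cautious. The dates are harder to rebuild once subjects have completed follow-up, so the fields are best added now. Nothing in this changes how patients are treated.

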Furthermore, there are other patient groups that represent a challenge to our current diagnostic tools. Patients with contrast dye allergy may need premedication that delays or sometimes even prevents those patients from receiving intravenous contrast. Typically, these patients would receive corticosteroids and antihistamines starting 13 hours prior to injection.^{11,12} However, even those that receive premedication can have contrast reactions.¹³ Patients with PE who have negative venous duplex ultrasound exams are sometimes suspected to have pelvic vein thrombi, or those with suspected chronic thromboembolic pulmonary hypertension or angiosarcomas of the

pulmonary arteries could benefit from a diagnostic tool that can image fresh intravascular thrombi and distinguish it from tumor or organized, endothelialized old thrombus.

All these shortcomings of current diagnostic strategies mean that physicians often are either uncertain whether a patient truly has an acute VTE or feels certain when none is present. These situations invariably lead to errors in diagnosis and lead to two dangerous problems. Either patients have an acute thrombosis and do not receive anticoagulation, putting them at risk for a deadly pulmonary embolus, or, they are subjected to anticoagulation unnecessarily and the significant risk of life-threatening hemorrhage.

The development of a fibrin-specific targeted diagnostic that identifies fresh thrombotic foci anywhere in the body has the potential to be a transformative tool for VTE assessment that would greatly enhance our diagnostic accuracy and capability for an extremely common and deadly disease. ^{64}Cu -FBP8 (Copper-64 labeled fibrin binding probe 8, Scheme 1) is a molecular imaging probe which selectively binds the main constituent of human thrombi: fibrin. Thrombus formation and fibrin deposition are pivotal events in several human conditions including major cardiovascular diseases, cancer, and inflammation. ^{64}Cu -FBP8 combines the high specificity of a fibrin-binding peptide and the great sensitivity and potential full-body applications of nuclear imaging. Studies in rats showed that ^{64}Cu -FBP8 has excellent pharmacological and pharmacokinetic profile, with high target uptake and low retention in background tissues and organs.¹⁴

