- No groups designated as “special vulnerable populations” will be studied.
- No exclusions will be made based on race, sex, or ethnic origin.
- ⁶⁴Cu-FBP8 (Copper-64 labeled fibrin binding probe 8) is cleared by the kidneys, patients with eGFR < 30 will be excluded.

IV. SUBJECT ENROLLMENT

Identification of eligible subjects will be done from 1) admissions to the Massachusetts General Hospital for treatment of pulmonary embolus (PE) 2) admissions to MGH for other indications but with an acute PE at admission or during hospitalization, 3) patients who present to the Emergency Department with an acute PE, but will not be admitted to the hospital. The subjects will be identified through the MGH Pulmonary Embolus Response Team (PERT), radiology notifications or running PeRC Epic team report, which could identify inpatients who were not picked by PERT or radiology notifications, or through patients physician investigators may be aware of that have an acute PE. PERT is a well-established group of cardiologists, pulmonologists, interventional radiologists, emergency room physicians, and cardiac surgeons who are “on-call” when a clinician anywhere in the hospital suspects a patient has a clinically significant pulmonary embolus. When PERT is activated, a fellow organizes a web-based meeting within minutes through a page and email to the participating physicians. The data is reviewed via “go-to-meeting” conference and a treatment plan is decided upon by consensus. An email will be sent to [name], and [name] when PERT is activated and [name] will assess whether the patient is appropriate and potentially eligible for the study. Also, since the fibrin probe must be manufactured at MGH Navy Yard and sent to MGH main campus, only patients diagnosed at a time when they can receive the radiotracer within 72 hours of their diagnosis will be included. If the patient meets eligibility criteria, the patient’s treating physician will be contacted to ask the patient for permission to be contacted by the study staff. During the first contact, the physician co-investigator will screen the subject for eligibility and describe the study and its implications, risks and benefits. If the subject is interested, the consent form will be given to the subject to read. The subject will be given as much time as necessary to decide, however if a decision cannot be made within the 72-hour limit from initial diagnostic imaging to the fibrin probe injection, or not before a scheduling time window for fibrin injection, the subject will be excluded. We will allow as much time as necessary for the subject’s questions to be answered or for the subject to consult family members or treating doctors before the consent form is signed. After the subject signs the consent form, the original signed consent form will be kept on file, a copy will be given to the subject, and a copy will be scanned to the subject EMR. No study procedures will be performed prior to the subject signing the informed consent document. The informed consent process will be accurately documented in the subject medical records.

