The standardized uptake value (SUV) of ⁶⁴Cu-FBP8 uptake in the lungs, pelvis and thighs will be calculated. The target to background ratio (TBR) for ⁶⁴Cu-FBP8 activity will be calculated using as background a region of interest (ROI) created from large cardiac and vascular structures. This corrects the ⁶⁴Cu-FBP8 activity for differences in injected dose and timing of imaging and allows for flexibility in the image timing. One member of our group ([name]) and another from Nuclear Medicine ([name]) will be blinded to the clinical results and will identify the presence or absence of clot in the three imaged locations as well as the anatomic location(s) and extent as best as possible from the overlay of the fibrin activity on the attenuation correction CT scans. Additionally, we will perform quantitative image analyses including the volume of the thrombus ROI, activity of imaged clot in each imaged section and clot burden. The thrombus ROI is defined by a threshold of 50% between peak activity of the ROI and background activity. Multiple ROIs will be used in the case of separated thrombi. Clot burden will be estimated using the sum of ⁶⁴Cu-FBP8 activity within a thrombus ROI and then normalized by the injected dose.

Outcome Measures:

Specific Aim 1: The location and extent of the thrombus region of interest (ROI), its volume and clot burden within the lung ROI will be compared with the ROI of filling defects on CT-angiogram. We will determine the number and location of the thrombus ROI(s) within the lungs, and the overall clot burden as sum of ^{64}Cu -FBP8 activity within a thrombus ROI(s) within the lungs. Additionally, we will calculate the intersection of the thrombus ROI and filling defects ROI relative to volume of the thrombus ROI. That will quantify the fraction of thrombus ROI(s) using a scale from being are completely outside (0) to completely inside (1). Also, we will perform a lung segmentation using the software APOLLO (VIDA Diagnostics) and determine in which lung lobe the thrombus ROI(s) are located.

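### The Aim 3 D-dimer correlation uses all in-field probe activity except four organs, unadjusted, so non-clot fibrin or shared comorbidity may create or distort it

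*Combined protocol and SAP*

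**What the plan says.** **Hypothesis.** II. Specific Aims, Aim 3, expects total clot burden on the fibrin scan to correlate with D-dimer.

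**D-dimer analysis.** VI. Biostatistical Analysis, Outcome Measures, Specific Aim 3, takes as its PET measure "the total fibrin activity in the imaged fields, excluding the liver, gallbladder, kidneys and urinary bladder normalized by injected dose for all patients", and this "will be correlated with the plasma D-dimer drawn at the time of imaging". It names no stratification, covariate or subgroup.

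**Clot burden.** The same section, under Specific data variables, defines clot burden more narrowly, as dose-normalised activity inside a thrombus region of interest (ROI): "The thrombus ROI is defined by a threshold of 50% between peak activity of the ROI and background activity".

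**Clinical outcomes.** The closing paragraph of Outcome Measures sets mortality, recurrent VTE and quality of life against burden on PET and on standard imaging. These comparisons are to be "stratified by treatment (systemic thrombolysis, catheter thrombolysis, or heparin alone) using multiple correlation, ANOVA, and t-tests for pairwise comparisons". Treatment is the only stratifier. No covariate is named.

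**Who can enrol.** I. Background and Significance states: "Thrombus formation and fibrin deposition are pivotal events in several human conditions including major cardiovascular diseases, cancer, and inflammation". IV. Subject Enrollment recruits, among others, "admissions to MGH for other indications but with an acute PE at admission or during hospitalization". III. Subject Selection excludes a pre-existing condition only where the investigator judges that it substantially raises risk. Cancer, infection and recent surgery are not exclusions in themselves.

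**What is recorded.** V. Study Procedures provides for a detailed history and a chart review. Its list of database variables has no field for cancer, infection, inflammatory disease or surgery.

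**The concern.** The measure correlated with D-dimer is not the clot burden in the hypothesis. Only the liver, gallbladder, kidneys and bladder are removed. Any probe uptake in a thoracic or pelvic tumour, an infected lung or a surgical wound would stay in the sum and count as clot.

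Separately, a comorbidity that raises both total activity and D-dimer would produce a correlation between them even if clot played no part. Either route would let the study report support for Aim 3 that is not evidence about clot. Because the study is meant to justify a larger one, the error would carry forward.

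For death and recurrence the route differs. Burden there is confined to thrombus ROIs, so the main worry is a comorbidity that raises both true clot load and the risk of the event. Treatment strata do not separate sicker from healthier patients within a stratum.

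**Working it through.** The plan gives no alpha, power, effect size, event rate or comorbidity prevalence, so it has no figure to reproduce. What follows is illustrative. Only N = 80 (III. Subject Selection) comes from the documents.

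**1. D-dimer correlation**

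Assume one binary comorbidity C with prevalence p. It shifts both total activity and D-dimer by d within-group SDs, and the two are otherwise unrelated. The covariance is then p(1−p)d² and each variance is 1 + p(1−p)d², so

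r = p(1−p)d² / [1 + p(1−p)d²].

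At N = 80, two-sided p < 0.05 requires |r| > 0.220. By Fisher's z, with z = atanh(r) × √77, the chance of significance is Φ(z − 1.96) + Φ(−z − 1.96).

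Example: p = 0.2 and d = 1 give r = 0.16/1.16 = 0.138, z = 1.22, and a 23% chance.

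| p | d | spurious r | chance of p < 0.05 |
|---|---|---|---|
| 0.1 | 0.5 | 0.02 | 5% |
| 0.1 | 1.0 | 0.08 | 11% |
| 0.2 | 1.0 | 0.14 | 23% |
| 0.3 | 1.0 | 0.17 | 34% |
| 0.3 | 1.5 | 0.32 | 83% |
| 0.4 | 1.5 | 0.35 | 90% |

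A simulation with 10,000 runs per setting gave these false-positive rates:

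| p | d | unadjusted | adjusted for C |
|---|---|---|---|
| 0.1 | 0.5 | 4.9% | 4.7% |
| 0.2 | 1.0 | 23% | 4.6% |
| 0.3 | 1.0 | 33% | 5.0% |
| 0.3 | 1.5 | 85% | 5.2% |

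**2. Death**

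Assume a cancer prevalence, one-year mortality with cancer and 5% without, a PET burden d SD higher with cancer, and no effect of clot on death. The spurious standardised difference between those who die and survivors is

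d × [P(cancer | died) − P(cancer | alive)].

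- **Base case** (20% cancer, 40% mortality, d = 0.5). Deaths: 0.2 × 0.40 + 0.8 × 0.05 = 12%, or 9.6 of 80. Difference: 0.5 × (0.667 − 0.136) = 0.265 SD.
- **Low corner** (15%, 30%, 0.25). Deaths 8.75%, or 7. Difference: 0.25 × (0.514 − 0.115) = 0.100 SD.
- **High corner** (25%, 50%, 0.75). Deaths 16.25%, or 13. Difference: 0.75 × (0.769 − 0.149) = 0.465 SD.

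In the base case the standard error is √(1/9.6 + 1/70.4) = 0.34. A nominal 5% test would then reject about 12% of the time. Over the grid the rate is about 6% to 34%.

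**3. Room for adjustment**

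Assumed 12-month event rates of 5% to 20% give 4 to 16 events in 80 patients. That supports one or two covariates at most.

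**The case against.** **The Background does not show that tumour or inflamed tissue takes up this probe.** It calls fibrin deposition pivotal in those states. The same section hopes the tool will tell fresh thrombus from tumour, and cites low background retention in rats. This stands in part. Those statements are an aim and animal data, so they do not exclude the problem, but they do rule out saying that comorbidity *does* confound. Nor do the documents say that cancer or inflammation raises D-dimer or mortality, or link surgery to uptake. These are assumptions.

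**A reader might infer that tumour uptake directly contaminates the death and recurrence analyses.** The text does not support this. The four-organ rule ("excluding the liver, gallbladder, kidneys and urinary bladder") belongs to the D-dimer analysis, while the outcomes use thresholded thrombus ROIs. Direct contamination is less certain there, though not excluded, because readers blinded to the clinical results locate clot on attenuation-correction CT. In the base case for death, the assumed bias (0.265 SD) is smaller than its standard error (0.34).

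**A reader might infer that the D-dimer correlation is stratified by treatment.** It is not. The stratification sentence covers death, recurrence and quality of life only.

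**The information is not lost.** History and record review are listed as research material and Medical History is a scheduled event. This stands: what is missing is a named analysis field. Likewise, multiple correlation could carry covariates, but none is specified.

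**This is a proof-of-concept study and no hypothesis concerns death or recurrence.** This stands for the outcome analyses. It does not dispose of the D-dimer analysis, which, although secondary, tests a stated Aim 3 hypothesis.

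**Conclusion.** The point holds for the D-dimer correlation. The plan tests a hypothesis about clot burden with a broader measure that can include non-clot fibrin, in a population where that is plausible, and without adjustment. Depending on values the documents do not give, the effect ranges from negligible (about a 5% chance of a significant result, the nominal rate) to decisive (about 90%). This rests on a single binary comorbidity, an equal and constant shift in both measures, and no other link between them.

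For death and recurrence the concern is secondary. Comorbidity may confound, with an illustrative spurious difference in burden of 0.10 to 0.465 SD for death, all inputs except N assumed. A reader might conclude that full multivariable adjustment is needed. With about 10 deaths under the assumed rates, the study could not support it.

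The comparisons of PET with CT angiography and ultrasound in Aims 1 and 2 are within-patient and do not depend on this.

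**What to change.** 1. Add three yes/no database fields, filled from the existing history and chart review: active cancer; acute infection or inflammatory disease; recent surgery or trauma, with the time window defined in advance.
2. Correlate D-dimer with thrombus-ROI clot burden as well as total-field activity. The Aim 3 sentence says *both* but names only one PET measure, so it needs rewording anyway.
3. Report the D-dimer result unadjusted, as a partial correlation on a single indicator (any of the three present), and again in subjects with none of the three. Keep the unadjusted result: where comorbidity acts by producing real clot, adjustment removes some genuine association.
4. After the blinded read is locked, flag uptake at documented non-thrombus sites and report total activity with and without it. Do not simply delete it, since true clot may lie there.
5. Label the death and recurrence analyses exploratory, with at most the single indicator as a sensitivity adjustment. Entering three fields and age separately would cost four degrees of freedom.

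**Cost:** three database fields, analysis wording, one degree of freedom and a smaller sensitivity set. No new visits, tests or subjects are needed.
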